5.2.4. Collected data

Defined algorithms are detailed in Appendix A.

5.2.4.1. Women characteristics

The following data will be extracted for the analysis population:

- Demographic characteristics: birth month and birth year, sex, region, practice identifier, family number, marital status, date of death (if applicable) and acceptable patient flag
- CPRD **GOLD** information: CPRD **GOLD** start date, current registration date, registration gaps, registration status
- History of previous pregnancies: parity and number of previous pregnancies
- Lifestyle during pregnancy: smoking, alcohol consumption
- Medical conditions during pregnancy: high blood pressure, diabetes
- Vaccines:

Administration of any other vaccine from 90 days before to 90 days after first day of gestation will be collected: date of vaccination, medcode and immunization type will

be extracted from the immunization file. Cross-tabulation of medcode and vaccine names/class is detailed in Appendix A.

- Vaccination with another vaccine within 90 days before first day of gestation or within the 90 days after first day of gestation (binary variable).
- Contra-indicated drugs during gestation:
The drugs used during the first trimester of gestation will be classified as: non contra-indicated drug, manufacturer advice “to use with caution” drugs, manufacturer mentioned advice “to avoid” drugs (this classification will be done respectively on the list of all drugs used during gestation reported in CPRD *GOLD* for each subject).

(Amended 14 March 2013)

5.2.4.2. Pregnancy outcomes

Pregnancy outcomes will be identified using defined algorithms (see Appendix A).

Definition of pregnancy outcomes (according to the UK or US definition):

1. Abortion defined as a loss of pregnancy with the first 23 weeks (≤ 161 days) or within the first 19 weeks (≤ 133 days) of gestation, with the following sub-categories:
 1. Spontaneous abortion
 2. Induced / therapeutic abortion
 3. Other abortion
2. Stillbirth defined as intra-uterine death of foetus after 23 weeks (>161 days) or after 19 weeks (> 133 days) of gestation
3. Live births, with the following sub-categories:
 1. Small for gestational age at birth
 2. Large for gestational age at birth
 3. Pre-term delivery (< 37 weeks of gestation)
 4. Full term delivery (between 37 weeks and 42 completed weeks of gestation)
 5. Post-term delivery (> 42 *completed* weeks of gestation)

(Amended 14 March 2013)

Confirmation of pregnancy outcomes (according to the UK or US definition):

For each pregnancy, the gestational age at outcome will be computed in days as:

- $\text{Gestational_age (days)} = (\text{date of outcome}) - (\text{date of first day of gestation}) + 1$

All abortions and stillbirths will be confirmed using this gestational age:

- if $\text{gestational_age} \leq 161$ days or ≤ 133 days, \rightarrow abortion is confirmed

- if gestational_age > 161 days or > 133 days, → stillbirth is confirmed

For all the identified cases of spontaneous abortion, other abortion, and stillbirth, the associated free text will be reviewed by a GSK-identified reviewer for sub-category classification (spontaneous, induced/therapeutic, and others). As far as possible, other abortion will be re-classified as spontaneous or induced/therapeutic abortion.

Cases of live birth will be classified as pre-term, full term and post-term delivery based on the gestational age at delivery:

- if gestational_age < 259 days then pre-term delivery is confirmed
- if gestational_age \geq 259 and \leq 294 days then full term delivery is confirmed
- if gestational_age > 294 days then post-term delivery is confirmed

Cases of live birth for which confirmation of pre-term, full term or post-term delivery is not possible because the gestational age is missing will be classified as non-confirmed pre-term, full term or post-term delivery, respectively.

Confirmation of cases of “small for gestational age at birth” and of “large for gestational age at birth” will be done as follows by comparing the weight and/or length at birth with the age and sex specific normal weight or length distributions. If the measured weight or length at birth is \leq 10th percentile of normal weight or length, the “small for gestational age at birth” will be confirmed. If the measured weight or length at birth is \geq 90th percentile of normal weight or length, the “large for gestational age at birth” will be confirmed.

Cases of “small for gestational age at birth” and of “large for gestational age at birth” identified in the codes but for which confirmation is not possible because both weight and length at birth are missing will be classified as non-confirmed “small for gestational age at birth” or non-confirmed “large for gestational age at birth”.

The GSK Safety physician will also review the following pregnancy outcomes: abortions (spontaneous abortions, induced/therapeutic abortions, other abortions), stillbirths, neonatal death, for live births: pre-term and post-term delivery, small for gestational age at birth or large for gestational age at birth.

(Amended 14 March 2013)

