Post Authorisation Safety Study:	A pharmacoepidemiological study or a clinical trial carried out in accordance with the terms of the marketing authorisation, conducted with the aim of identifying or quantifying a safety hazard relating to an authorised medicinal product. This includes all GSK sponsored non-interventional studies and clinical trials conducted anywhere in the world that are in accordance with the terms of the European marketing authorisation and where the investigation of safety is the specific stated objective. Note: The phrase, ‘In accordance with the terms of the European marketing authorisation’ means that the product is used according to the European label (e.g. within the recommended dose range, the approved formulation, indication etc.).

Post-term delivery:	Delivery after 42 completed gestational weeks (\geq 43 gestational weeks).
Pregnancy onset:	Pregnancy onset is defined as the first day of LMP plus 14 days (two weeks).
Pre-term delivery:	Delivery at less than 37 completed gestational weeks.
Small for gestational age:	Small newborn size defined as less than, or equal to, the 10 th percentile for sex and age on birth weight or length.
Spontaneous abortion:	Spontaneous loss of pregnancy during the first 23 weeks of gestation (UK definition). Spontaneous loss of pregnancy during the first 19 weeks of gestation (US definition).
Stillbirth:	Intra-uterine death of foetus in pregnancies 24 weeks or later of gestation (UK definition) Intra-uterine death of foetus in pregnancies 20 weeks or later of gestation (US definition)
Subject:	Term used throughout the protocol to denote an individual who has been contacted in order to participate or participates in the clinical/ epidemiology study, or a person about whom some medical information has been recorded in a database.
Targeted Safety Study:	Studies specifically planned or conducted to examine an actual or hypothetical safety concern in a product marketed anywhere in the world. This includes any GSK sponsored pharmaco-epidemiology study or clinical trial conducted anywhere in the world with the aim of identifying or quantifying a safety hazard. Although all clinical trials collect safety information as a matter of routine, only those initiated to examine a specific safety concern are considered a targeted safety study.

TRADEMARKS

The following trademarks are used in the present protocol.

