5.1.2. Secondary endpoints

- Occurrence of spontaneous abortion during weeks 1-19 of gestation
- Occurrence of other pregnancy outcomes:
 - Induced/therapeutic and other abortions (according to UK and US definitions of spontaneous abortion)
 - Stillbirth (according to UK and US definitions of stillbirth)
 - Birth defects identified among all pregnancies with known outcome classified as live births, stillbirths and abortions. For live births, birth defects identified within the first 12 weeks of life will be included
 - Small/Large for gestational age at birth
 - Pre-term and post-term delivery
- Baby's death in the first 12 weeks of life.

² Refer to GLOSSARY OF TERMS for definition of spontaneous abortion and of the other pregnancy outcomes

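### The confirmation rule in section 5.2.4.2 has no branch for type of loss, so terminations after the day cut-off fall into the secondary stillbirth endpoint unless a reviewer departs from it

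*Combined protocol and SAP*

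**What the plan says.** Section 5.2.4.2 computes gestational age in days at the outcome and then applies one rule to every loss: "All abortions and stillbirths will be confirmed using this gestational age". At or below the cut-off, abortion is confirmed. Above it, "if gestational_age > 161 days or > 133 days, → stillbirth is confirmed". Neither branch carries a condition on type of loss.

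The definitions earlier in the same section are narrower. Abortion, with its spontaneous, induced/therapeutic and other sub-categories, is limited to 161 days (UK) or 133 days (US). For the other outcome the text reads "Stillbirth defined as intra-uterine death of foetus after 23 weeks (>161 days) or after 19 weeks (> 133 days) of gestation". The Glossary also defines stillbirth as intra-uterine death. Section 5.1.2 makes induced/therapeutic abortion and stillbirth secondary endpoints, each counted under both national definitions.

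Three reviews follow the rule:

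- Free-text review (5.2.4.2): "For all the identified cases of spontaneous abortion, other abortion, and stillbirth, the associated free text will be reviewed" to assign the type of loss. Coded induced/therapeutic abortions are not on this list.
- Safety physician review (5.2.4.2): covers all abortion types, including induced/therapeutic, and stillbirths.
- Expert review (5.2.6): two experts blinded to HPV vaccine exposure make the final ascertainment of spontaneous and other abortions, stillbirths and babies' deaths. If they cannot agree, their opinions are listed.

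**The concern.** A termination is not an intra-uterine death as the plan uses the term, but the rule has only two outputs, and past the cut-off the only one available is stillbirth. A termination on day 150 would be an induced abortion in the UK tables and a stillbirth in the US tables of the same report.

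Stillbirth is a rare and serious safety outcome, to be compared between cohorts by logistic regression if there are at least 10 cases (5.6.3.2). Terminations may differ between cohorts for reasons unrelated to foetal death. When the true count is small, even a few of them change what the proportion and odds ratio measure. The induced/therapeutic abortion count loses the same women.

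**Working it through.** **Cut-offs.** 23 × 7 = 161 and 19 × 7 = 133. Gestational age is the date difference plus 1, so these are the last days of weeks 23 and 19. The plan's figures reproduce exactly and are not in question.

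**Tracing each kind of loss through the written rule**

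| Record | UK rule | US rule | Fits the plan's stillbirth definition where so labelled? |
|---|---|---|---|
| Termination, day 133 or earlier | abortion | abortion | not labelled stillbirth |
| Termination, days 134-161 | abortion | stillbirth | no |
| Termination after day 161 | stillbirth | stillbirth | no |
| Spontaneous loss, days 134-161 | abortion | stillbirth | yes |
| Spontaneous loss after day 161 | stillbirth | stillbirth | yes |

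Only the second and third rows are wrong. Every termination past day 161 is also past day 133, so the US count is affected at least as much as the UK count.

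**Effect on the primary analysis.** Sections 5.2.5.3 and 5.6.3.1 censor a woman still pregnant at the cut-off on day 161 (or 133), whatever happens later. A termination on days 134-161 is censored at its own date in the UK analysis and at day 133 in the US analysis. In neither case does the stillbirth label enter, so late terminations leave the spontaneous-abortion hazard ratios unchanged. Model 4, which counts any abortion before week 24, is likewise unaffected by terminations after day 161.

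**Possible size for US-definition stillbirth**

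Inputs from the documents:
- Pregnancies: 243 exposed (-30 to +45 days) + 667 non-exposed = 910 (section 3.2).
- Spontaneous abortion: 11.5% (section 5.4).

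Assumptions, because the documents give no figures:
- 20-50% of pregnancies terminated.
- 1-2% of those terminations after week 19.
- Stillbirth in 0.5% of continuing pregnancies.
- No review corrects any record.

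Late terminations = 910 × share terminated × share late. True stillbirths = 910 × (1 − share terminated − 0.115) × 0.005.

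| Terminated | Late | Late terminations | True stillbirths | Total | Termination share |
|---|---|---|---|---|---|
| 20% | 1% | 1.82 | 910 × 0.685 × 0.005 = 3.12 | 4.94 | 37% |
| 20% | 2% | 3.64 | 3.12 | 6.76 | 54% |
| 50% | 1% | 4.55 | 910 × 0.385 × 0.005 = 1.75 | 6.30 | 72% |
| 50% | 2% | 9.10 | 1.75 | 10.85 | 84% |

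The 10-case threshold is passed only in the last row. For the -30 to +90 day window the total is 379 + 667 = 1,046, so every count scales by 1,046/910 = 1.15. The last row is still the only one above 10 (12.5; the next highest is 7.8).

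**The case against.** The strongest reply is that the day rule is not the end of the process. Free-text review, which follows it directly, covers stillbirths and exists to say whether a loss was spontaneous or induced. The safety physician sees both induced abortions and stillbirths. The blinded experts see stillbirths for final ascertainment. A late termination relabelled as a stillbirth could be caught at any of these steps. Whether the free-text list is drawn up before or after the day rule is unclear, so it is not established that such records escape review. Outcome identification also relies on Appendix A, of which the public document shows only the title and some amended lines.

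Much of this stands. A reader might infer that gestational age alone settles the outcome, and the documents do not support that. What the reviews lack is a rule. None states that it may override the day cut-off. A reviewer who finds that a stillbirth was a termination has nowhere to put it, because the only induced category is itself capped at 161 or 133 days.

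A reader might also infer that late miscarriages are wrongly turned into stillbirths and removed from the primary endpoint. A spontaneous loss truly past the cut-off is a stillbirth by the plan's own definition. Only a misdated loss would be an error. Section 5.2.5.2 corrects dating by ultrasound where a scan exists, and spontaneous abortions, other abortions and stillbirths all go to the experts already. The documents give no frequency of misdating, so no effect on the primary result is claimed. The remaining gap is that nothing says which prevails when code and computed age conflict.

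**Conclusion.** The point holds for terminations after the cut-off. As written, the rule contradicts the plan's definition of stillbirth and can count such terminations in the secondary stillbirth endpoint while removing them from induced/therapeutic abortion, mainly under the US definition. Under the stated assumptions, and if no review corrects anything, about 2-9 terminations would join about 2-3 true US-definition stillbirths, or 37-84% of the total. These counts show what is possible and are not predictions. Passing the 10-case threshold because of terminations needs the most extreme pair of assumptions. Terminations after day 161 under the UK definition are not quantified separately.

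Severity is moderate: secondary endpoints only. A stronger grading would need an effect on the primary hazard ratio, which late terminations do not have, or evidence that the three reviews leave the errors in place, which the documents do not give. If the full Appendix A already branches on type of loss, the remaining task is to bring 5.2.4.2 into line with it.

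**What to change.** Before database lock, amend section 5.2.4.2 as follows:

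- Apply the 161/133-day split only to spontaneous intra-uterine deaths.
- Keep induced/therapeutic abortions in their own category at any gestation under both definitions, and amend the capped abortion definition to match.
- State that the final ascertainment in 5.2.6 overrides the day rule, including where a spontaneous or other abortion code conflicts with the computed age.

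The cost is a few sentences and a change to the derivation program. No new data are needed. Spontaneous and other abortions and stillbirths already go to the experts, so the review load should hardly change.

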Eligible:	Qualified for enrolment into the study based upon strict adherence to inclusion/exclusion criteria.
Epoch:	An epoch is a well-defined part of a protocol that covers a set of consecutive time points. Generally, an epoch is self-contained and allows to perform a data analysis to address some of the trial objectives (e.g. primary, booster, yearly follow-ups, retrospective data collection, prospective data collection).
eTrack:	GSK's tracking tool for clinical/epidemiology trials.
First trimester of pregnancy:	Time period extending from the first day of the last menstrual period (LMP) through 13 completed weeks of gestation.
Full-term delivery:	Delivery occurring ≥ 37 and ≤ 42 gestational weeks.

Gestational age:	Foetal age calculated from the first day of the LMP. It could be adjusted based on ultrasound at the first trimester of pregnancy. This involves the assumption that conception (fertilization) occurred 14 days later.
Large for gestational age:	Large newborn size defined as more than, or equal to, the 90 th percentile for sex and age on birth weight or length.
HPV vaccination catch-up programme:	Vaccination of a cohort of young women in addition to those targeted in the universal mass vaccination programme recommended by national Governments, as appropriate.
Independent Scientific Advisory Committee (ISAC):	Independent Scientific Advisory Committee for Medicines and Healthcare products Regulatory Agency database research . All studies that will be released into the public domain require ISAC approval. Every member is appointed by NHS.
Last menstrual period (LMP):	Considered as the first day of the LMP before conception (fertilization) onset. The first day of LMP is equal to first day of gestation. The estimated day of conception (fertilization) is calculated as the first day of LMP plus 14 days.
Live birth:	The foetus is born alive.
Non-interventional (observational) Human Subject Research:	Studies where medicinal products, should they be administered, are prescribed in normal (routine) medical practice. No medical care or medical/scientific procedures as required in a research protocol are administered to participants except as part of routine medical care.

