5.5.3.2. Other endpoints

All other endpoints are binary variables: stillbirths, live births, full term delivery, pre-term and post-term delivery, small for gestational age, large for gestational age, birth defects and baby's death.

The proportion of each outcome will be computed for the exposed and non-exposed cohorts as the number of cases divided by the total number of subjects with known pregnancy outcome. An exact 95% CI will be computed.

The exposed and non-exposed cohorts will be compared using logistic regression with the pregnancy outcome as the dependent variable, a dichotomous exposure as the independent variable and the age at first day of gestation as a covariate. The odds ratio (OR) and its 95% CI will be derived.

Baby characteristics will be summarized per cohort using descriptive statistics: n of non-missing observations, mean, standard deviation, minimum and maximum for continuous variables (birth weight and length) and frequency table (n, %) for categorical variables (sex, Apgar score at 1 and 5 min).

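### Small- and large-for-gestational-age rates are taken over all known outcomes or all pregnancies, so they vary with live-birth share and record completeness as well as with fetal size

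*Combined protocol and SAP*

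**What the plan says.** Section 5.2.4.2 lists small and large for gestational age as sub-categories of live birth and confirms them "by comparing the weight and/or length at birth with the age and sex specific normal weight or length distributions". Either measure is sufficient: the rule opens "If the measured weight or length at birth is" and then gives the 10th (or 90th) percentile cut. The Glossary has the same rule, "percentile for sex and age on birth weight or length", so the definition is consistent and evidently intended. A coded case is set aside as non-confirmed only where it is one "for which confirmation is not possible because both weight and length at birth are missing".

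The denominator is much wider than live births. Section 5.5.3.2 computes each proportion "as the number of cases divided by the total number of subjects with known pregnancy outcome". Section 5.6.2 uses the total number of pregnancies instead. Section 5.6.3.2 fits a logistic model with exposure and age at first day of gestation, excludes other covariates, and names no analysis set specific to these two outcomes. Section 5.6.1 says only that missing values are not replaced.

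**The concern.** A pregnancy that ends in abortion or stillbirth cannot yield a small or large live-born baby under section 5.2.4.2. A live birth with neither weight nor length recorded cannot be confirmed as one. Under the stated denominators both sit with the babies who were measured and found to be of normal size. The reported proportion is then a product of three things: the share of pregnancies ending in live birth, the share of live births with a recorded size, and the rate of small or large size. Only the third is the endpoint.

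If either of the first two differs between cohorts, the OR moves away from 1 with no effect on fetal growth, or a real effect is masked. Adjustment for age does not remove this. The live-birth share is also tied to the study's own hypothesis, because an excess of spontaneous abortion in the exposed cohort would lower it.

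A second, smaller issue is that a baby with both measures recorded has two chances to qualify and a baby with one has a single chance.

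**Working it through.** **Plan figures.** The documents state no expected rate for these endpoints, no completeness of weight or length, and no weight–length correlation, so there is no figure to reproduce. Every rate below is an assumption unless a source is given.

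**Denominator.** Let L be the live-birth share, m the share of live births with a recorded size, and q the true rate among live births. The reported proportion is p = L × m × q, and OR = [p1/(1−p1)] / [p0/(1−p0)]. Take q = 10% in both cohorts, so the true OR is 1.

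- Recording differs (L = 1; m = 90% vs 70%): p = 9% vs 7%. OR = (0.09/0.91)/(0.07/0.93) = 0.0989/0.0753 = 1.31.
- Live-birth share differs (m = 1; L = 60% vs 50%): p = 6% vs 5%. OR = (0.06/0.94)/(0.05/0.95) = 0.0638/0.0526 = 1.21.
- Link to the primary hypothesis. Section 5.4 uses an 11.5% spontaneous abortion rate and a relative risk of 2.0. Treating 2.0 as a risk ratio, with no other losses and m = 1, L = 1 − 0.23 = 0.77 exposed and 1 − 0.115 = 0.885 non-exposed. Then p = 7.70% vs 8.85%, and OR = 0.0834/0.0971 = 0.86. A real harm on the primary endpoint would look mildly protective here.
- Measured live births only: p = 10% vs 10%, OR = 1.00 in all three cases.

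**Either-measure rule.** Assume bivariate normal weight and length scores matching the reference, with every live birth classified. With both measured, P(either at or below the 10th percentile) = 0.10 + 0.10 − P(both).

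| Correlation | P(both) | P(either) |
|---|---|---|
| 0.6 | 0.0390 | 16.1% |
| 0.7 | 0.0468 | 15.3% |
| 0.8 | 0.0562 | 14.4% |

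With one measure the figure is 10%. If weight is always recorded and length in a fraction f, the rate is 0.10 + f × [P(either) − 0.10]. At correlation 0.7 and f = 60% vs 40%, this is 13.19% vs 12.13%, an OR of 1.10 (1.09 at correlation 0.8, 1.12 at 0.5). At f = 80% vs 50%, the OR is 1.16 (correlation 0.6) or 1.12 (0.8). With equal f the OR is 1.00.

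**Precision.** Take all 243 and 667 women in section 3.2 as measured live births, which is generous, with a 13% rate in both cohorts. The SE of log OR is √[1/(243 × 0.13 × 0.87) + 1/(667 × 0.13 × 0.87)] = 0.223. The 95% interval around 1 is exp(±1.96 × 0.223), about 0.65 to 1.55.

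**The case against.** The strongest reply is that nothing in the documents shows a difference between cohorts in recording or in live-birth share. Both cohorts are vaccinated women from one database release, one study period and one age range. With equal shares in both cohorts the OR stays at 1 when there is no effect. All the illustrative ORs also lie inside the 0.65 to 1.55 interval. This stands as a limit on size. It does not rescue the stated proportion, which understates the rate among measured babies whenever some pregnancies do not end in live birth or some babies are unmeasured.

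Some protection is already planned. Section 5.5.3.2 reports non-missing counts for birth weight and length per cohort, section 5.5.2 reports mother–baby linkage, and the safety physician reviews these cases. These would reveal an imbalance but do not correct the proportion or the OR.

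A reader might also infer that the either-measure rule labels well over 10% of normal babies as small, or as large. The documents do not support this as a general statement. It needs both measures recorded and every live birth classified, whereas section 5.2.4.2 speaks of confirming cases and of those "identified in the codes but for which confirmation is not possible", which can mean coded cases only. The algorithms are assigned to Appendix A, which is listed but not reproduced in the public text. The wide denominator may also pull the reported figure below 10%. Nor does the plan compare its rates with 10%.

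A further inference, that one baby could be both small and large, is arithmetically negligible: about 0.05% at correlation 0.6 and less at higher values. Finally, replacing the definition by weight alone is a preference. The plan's definition is deliberate, and weight alone would drop babies with only length recorded.

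**Conclusion.** The denominator point holds. The two stated denominators differ from each other, and neither is the set of babies in whom the endpoint can be observed. For the proportion this follows directly from sections 5.5.3.2 and 5.6.2. For the OR it follows because no other analysis set is given. Under the assumed imbalances the spurious OR is 1.21 to 1.31. It is 0.86 if the exposed cohort had the doubled abortion risk used for the power calculation and no other losses. The actual size cannot be derived from the documents.

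The either-measure rule is a lesser matter: about 14 to 16% against 10%, conditional on full classification and an assumed correlation of 0.8 to 0.6, with between-cohort bias only under differential recording. It calls for a sensitivity analysis and does not justify changing the definition.

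The change should be made before analysis. It concerns two secondary endpoints and leaves the primary result untouched.

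**What to change.** - **Sections 5.5.3.2, 5.6.2 and 5.6.3.2:** for small and large for gestational age, use one analysis set for both the proportion and the logistic model, namely live births with gestational age and at least one recorded size measure.
- **Section 5.2.4.2:** state that every such live birth is classified, not only those carrying a code. Show non-confirmed coded cases on a separate line, outside the main proportion.
- **Definition:** keep weight or length as written. Add a sensitivity analysis on birth weight alone among live births with recorded weight.

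The cost is wording, programming, a smaller denominator and one extra analysis. The result must be read as conditional on live birth and on having been measured. The non-missing counts already planned per cohort should be shown beside it so that any imbalance in recording is visible.
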